Study design	Prospective, open label, non-randomized, multicenter, blinded pathology assessment study to evaluate the tolerability and the diagnostic utility of Lymphoseek in pediatric subjects with melanoma, rhabdomyosarcoma, or other solid tumors. Subject age will range from neonatal through 17 years. If consistent with institutional practice, subjects may also receive Lymphazurin for a within-subject comparison of lymph node mapping.
Methodology	The proposed study includes 3 visits: A screening visit for initial determination of eligibility and evaluation of clinical status, a baseline visit on the day of surgery, and a 4- to 14-day (in person) safety follow-up to assess subject disease management.
	Screening Visit (Day -29 to 0):
	The screening visit will include review of trial eligibility, demography, performance status, cancer staging, informed consent, collection of medical history, vital signs, physical exams, electrocardiogram (ECG), review of medications, and clinical laboratory evaluation. A urine or serum pregnancy test will be performed for female subjects of childbearing potential within 48 hours prior to injection.
	Baseline Visit (Day 1):
	All subjects will receive a single dose of 50 μ g Lymphoseek radiolabeled with 18.5 MBq (0.5 mCi) ^{99m} Tc (in a volume of up to 1.0 mL) at least 15 minutes but no more than 8 hours before the start of the surgical procedure.
	For subjects with melanoma, Lymphoseek will be administered as 1 to 4 intradermal, peritumoral injections or around the excision biopsy site. For subjects with rhabdomyosarcoma or other solid tumor type, Lymphoseek will be administered as intradermal peritumoral injection(s) if anatomically appropriate or, if not possible, injection should be performed as determined clinically appropriate by the surgeon. Radioactive dose, volume, injection site(s), route, and syringe type will be documented.
	An ECG will be recorded on Day 1 at least 10 minutes after Lymphoseek injection. Vital signs will be recorded at prespecified intervals before and after Lymphoseek administration.
	After safety measurements have been completed and before surgery, subjects may undergo dynamic and/or planar SPECT or SPECT/CT lymphoscintigraphy according to

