7.2.6 Day 1: Post Injection

Vital signs will be collected at 10 minutes, 30 minutes, and 1 hour post-injection and after surgery. Vital signs will include body temperature (°F or °C), respiratory rate, pulse rate, and systolic and diastolic blood pressures. Before blood pressures and pulse are obtained, the subject should be resting quietly for 1 minute. Body weight and height measurements are not required. Allowable windows for vital sign collection are as follows:

 $0:10, 0:30 = \pm 3$ minutes 1:00 hour $= \pm 5$ minutes An ECG will be recorded on Day 1 at least 10 minutes after Lymphoseek injection. The ECG reading will be reviewed by the investigator, and any clinically significant abnormal findings will be noted as an AE.

Each syringe will be assayed individually and recorded in the source documentation after injection.

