7.2.7 Day 1: Imaging and Surgery

Dynamic and/or planar SPECT or SPECT/CT imaging may be performed prior to surgery as described in Section 8.3, and any finding will be documented and recorded on the appropriate CRF.

Vital signs and ECGs will be recorded as described in Section 7.2.6.

If Lymphazurin is to be used, it should be administered in the operating room at the start of or during surgery prior to transcutaneous surveying. The injection will be performed as deemed appropriate by the surgeon and in accordance with the standard of care at the clinical site. Fifteen minutes to 8 hours after Lymphoseek injection, subjects will undergo surgery to remove the primary tumor, ILM will be performed, and SLN(s) will be harvested. Locations of both hot and blue (when applicable) nodes will be recorded.

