8.7.2.2 Vital Signs

Vital signs comprise the measurement of systolic and diastolic blood pressure, body temperature, respiration, and heart rate. All vital signs will be measured after the subject should be resting quietly for 1 minute. Heart rate should be measured immediately before or immediately after blood pressure measurement.

Vital signs will be measured at screening, baseline (before investigational product injection), 10, 30, 60 minutes post injection (Day 1), and at the 4- to 14-day follow-up visit.

Any clinically significant change from baseline that results in a change in subject management will be considered an AE.

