8.7.2.3 Electrocardiogram

A standard 12-lead ECG will be obtained at screening and on Day 1 at least 10 minutes after Lymphoseek injection. The ECG will be measured with the subject in a resting position for at least 1 minute. No continuous ECG monitoring will be required.

On-site investigator's responsibilities

The immediate cardiac safety of the subject will be ensured by the on-site qualified physician. Any 12-lead ECG intervals, waveform abnormalities, and rhythm changes that are clinically significant in that they result in a change in subject management will be considered an AE. In the case of an SAE, once SAE notification is decided upon, investigators are required to follow the procedure described for SAE notification and document abnormal ECG findings (intervals and waveforms). Any interval data or abnormal waveform finding that resulted in an AE (i.e., change of patient management) must be followed for the duration of the subject's participation in the study until normalization or return to baseline takes place.

Each 12-lead ECG tracing must be signed and dated and stored in the subject's source documentation.

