9.9.4 Analysis of Secondary Safety Variables

Summary statistics (mean, median, sample size, standard deviation, minimum, and maximum) will be computed on the raw and change from baseline values for each vital sign parameter by time point, for each tumor type and overall. The pre-injection time point will serve as baseline. If there are multiple vital signs taken at any time point, then the latest set of vital signs will be used for the analysis. All vital sign data will be listed.

Summary statistics (mean, median, sample size, standard deviation, minimum, and maximum) will be computed on the raw and change from baseline values for each quantitative laboratory parameter by time point, for each tumor type and overall. The screening time point will serve as baseline. If there are multiple labs taken at any time point, then the latest set of labs will be used for the analysis. All clinical laboratory data, including any qualitative urinalysis results, will be listed.

Summary statistics (mean, median, sample size, standard deviation, minimum, and maximum) will be computed on the raw and change from baseline values for each ECG parameter by time point, for each tumor type and overall. The screening time point will serve as baseline. If there are multiple ECGs taken at any time point, then the latest set of ECGs will be used for the analysis. All ECG data will be listed.

Additional analyses of safety variables for this study may be conducted as described in the Statistical Analysis Plan document.

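### The 30- and 60-minute vital signs and the Day 1 ECG can be taken during anaesthesia or surgery, and section 9.9.4 summarizes them without separating those readings

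*Combined protocol and SAP*

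**What the plan says.** **Timing of readings.** Section 7.2.6 requires: "Vital signs will be collected at 10 minutes, 30 minutes, and 1 hour post-injection and after surgery". It allows 3 minutes either side of the 10- and 30-minute readings and 5 minutes either side of the 1-hour reading. It also states: "An ECG will be recorded on Day 1 at least 10 minutes after Lymphoseek injection". Section 8.7.2.3 repeats this lower limit, and neither section gives an upper one. Appendix 1 marks the Day 1 ECG in the 1:00 column.

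**Timing of surgery.** Section 7.2.7 says: "Fifteen minutes to 8 hours after Lymphoseek injection, subjects will undergo surgery". The synopsis (Methodology, Baseline Visit) likewise has the injection given "at least 15 minutes but no more than 8 hours before the start of the surgical procedure", and footnote f of Appendix 1 agrees. Section 7.2.7 refers back to 7.2.6 for vital signs and ECG and does not tie them to induction or incision.

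**Order of events.** The synopsis and section 8.3 place optional lymphoscintigraphy after the safety measurements and ahead of surgery. Section 8.3 also lets dynamic imaging begin at injection and asks that imaging finish within 60 minutes.

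**Analysis.** Under section 9.9.4, summary statistics are "computed on the raw and change from baseline values for each vital sign parameter by time point", for each tumor type and overall. Baseline is pre-injection for vital signs and screening for ECG. If a time point has several readings, the latest is used. All data are listed.

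**Anaesthesia.** Sections 7.2.8 and 8.1.5 say that anaesthetic drugs given for surgery need not be entered in the eCRF.

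**After-surgery reading.** Section 8.7.2.2 lists screening, baseline, "10, 30, 60 minutes post injection (Day 1), and at the 4- to 14-day follow-up visit", with no after-surgery reading. Appendix 1 has no vital-signs mark in its After Surgery column.

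**The concern.** Changes in vital signs and ECG are the secondary safety endpoints of a study whose primary objective is safety. A child whose surgery starts early may be anaesthetised at 30 or 60 minutes, while a child whose surgery starts hours later is awake. Section 9.9.4 averages the two at the same nominal time. Section 7.2.6 asks for a minute of quiet rest before blood pressure and pulse, but that does not record which state the child was in.

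The study has a single arm, so no control group carries the same anaesthetic effect. Because anaesthetic drugs need not be captured, the medication data may not identify the affected readings. A mean fall in pressure or heart rate at 30 or 60 minutes, or an ECG change, could then be read as a drug effect when it is anaesthetic or surgical. The reverse could also happen.

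The difference over the after-surgery reading is a separate matter: sites may collect it or not, depending on which section they follow.

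**Working it through.** **1. Can the readings overlap with surgery?** The inputs are the windows in 7.2.6 and the earliest surgery start of 15 minutes (synopsis, 7.2.7, Appendix 1 footnote f).

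| Reading | Window (min) | Latest time minus 15 min | Can follow surgery start? |
|---|---|---|---|
| 0:10 | 7 to 13 | 13 - 15 = -2 | No |
| 0:30 | 27 to 33 | 33 - 15 = 18 | Yes, by up to 18 min |
| 1:00 | 55 to 65 | 65 - 15 = 50 | Yes, by up to 50 min |
| ECG | from 10 (text); 1:00 (Appendix 1) | 60 - 15 = 45 at the 1:00 mark | Yes, on either statement |

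The documents give no induction time. If induction precedes the start of surgery, the period at risk begins earlier, and the 10-minute reading could fall within it.

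**2. Does any passage make surgery wait?** The only candidate is the sentence in the synopsis and 8.3 that puts safety measurements before imaging and imaging before surgery. It introduces a procedure that subjects may undergo and sets no rule for subjects who are not imaged. Suppose it did mean that all readings through 1:00 come first. Imaging could then not begin before 55 minutes, yet 8.3 lets it begin at injection, the synopsis has static imaging begin at about 15 minutes, and 8.3 has imaging end by 60 minutes, while the 1-hour window runs to 65. Surgery at 15 minutes would also be impossible. So the sentence does not remove the overlap; it adds a conflict.

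**3. How many subjects might be affected?** The documents do not say. For illustration only, assume that surgery start is uniform from 15 to U minutes and that surgery is still under way at the reading. The share whose surgery has started by minute t is (t - 15)/(U - 15).

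| U (min) | t = 30 | t = 60 |
|---|---|---|
| 480 | 15/465 = 3% | 45/465 = 10% |
| 240 | 15/225 = 7% | 45/225 = 20% |
| 120 | 15/105 = 14% | 45/105 = 43% |
| 60 | 15/45 = 33% | 45/45 = 100% |

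**4. How far would the mean move?** With a share f affected and an anaesthetic change d, the shift in mean change is f × d. Both f and d are assumptions; d is taken as -10 to -20 mmHg systolic.

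- f = 0.10: -1 to -2 mmHg
- f = 0.25: -2.5 to -5 mmHg
- f = 0.50: -5 to -10 mmHg
- one subject in a tumor stratum of 6 (the planned minimum for melanoma and for rhabdomyosarcoma): -10/6 = -1.7 to -20/6 = -3.3 mmHg

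No size is computed for the ECG, because the documents give nothing to base one on. Its baseline is screening (Day -29 to 0), so its change from baseline already compares different days.

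**The case against.** The best case against runs as follows. A site that follows the sequencing sentence in the synopsis and 8.3 would finish the safety measurements before operating, at least in imaged subjects. If surgery starts were spread evenly over the permitted 15 to 480 minutes, only about 3% of subjects would be in surgery at 30 minutes and 10% at 60. The summaries are descriptive, with no test or threshold. The primary safety variable is adverse event incidence, and clinically significant changes that alter management become adverse events. All readings are listed, so outliers stay visible. Section 9.9.4 also allows further safety analyses in a statistical analysis plan, and the text available here holds no separate plan, so a split may be specified there.

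Much of this stands, and it limits how serious the point is. It does not remove the point: nothing in the text makes surgery wait, and 9.9.4 as written has no split.

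A reader might go further and infer one of the following:

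- **Every post-injection reading is compromised, so a drug effect could be hidden throughout.** The documents do not support this. The 10-minute window closes 2 minutes before surgery may start.
- **The ECG has no scheduled time.** The text of 7.2.6 and 8.7.2.3 has no upper limit, but Appendix 1 places the ECG at 1:00. This is a conflict to reconcile, not an absence.
- **A large share of readings is affected.** Shares of 30% or 50% need surgery starts clustered early, which the documents do not show.
- **The main summary should use pre-induction readings only.** At 30 and 60 minutes that would select subjects with later surgery and thin strata of about 6.

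**Conclusion.** The point holds in a limited form. The plan permits the 30- and 60-minute vital signs and the Day 1 ECG to be taken during anaesthesia or surgery, and 9.9.4 does not distinguish those readings. The descriptive secondary safety summaries can therefore mix anaesthetic and surgical effects with any effect of Lymphoseek. That the overlap is permitted follows from the documents alone. Its frequency is not stated, and the shifts of -1 to -10 mmHg rest on an assumed fall of 10 to 20 mmHg and an assumed 10% to 50% of subjects affected. The primary safety variable is not directly at issue. The contradiction over the after-surgery vital signs is certain and needs no assumption. The change is worth making because it costs little and the study has no control arm to separate the effects.

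**What to change.** **Data.** Record the time of induction (or, failing that, the start of surgery) and the actual time of each Day 1 vital sign and ECG. Flag each Day 1 post-injection reading as before or after induction. If the start of surgery stands in for induction, say so, because readings between the two would be counted as before.

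**Analysis.** In 9.9.4 keep the all-subject summary as planned and add the same summary split by the flag. Show the flag in the vital-sign and ECG listings. State beside the table that cells will be small and that the pre-induction group at 30 and 60 minutes consists of subjects with later surgery, so the two groups are not comparable in other respects.

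**Text to reconcile,** without this review saying which clinical timing is right:

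- 7.2.6, 8.7.2.2 and Appendix 1 on vital signs after surgery
- 7.2.6 and 8.7.2.3 against Appendix 1 on ECG timing
- the sequencing sentence in the synopsis and 8.3 against the imaging, vital-sign and surgery times

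**Cost.** A few eCRF time fields if not already captured, one added table split and one listing column. Amendment 4 is dated September 2017 and the planned start was August 2015, so times for subjects already treated may have to be retrieved from source records. No change to surgical timing is needed.

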7.2.7 Day 1: Imaging and Surgery

Dynamic and/or planar SPECT or SPECT/CT imaging may be performed prior to surgery as described in Section 8.3, and any finding will be documented and recorded on the appropriate CRF.

Vital signs and ECGs will be recorded as described in Section 7.2.6.

If Lymphazurin is to be used, it should be administered in the operating room at the start of or during surgery prior to transcutaneous surveying. The injection will be performed as deemed appropriate by the surgeon and in accordance with the standard of care at the clinical site. Fifteen minutes to 8 hours after Lymphoseek injection, subjects will undergo surgery to remove the primary tumor, ILM will be performed, and SLN(s) will be harvested. Locations of both hot and blue (when applicable) nodes will be recorded.

7.2.8 Day 1: After Surgery

Clinical laboratory evaluations (chemistry, hematology and urinalysis), review of medications, and AE monitoring will be performed. Medications administered for anesthesia related to surgery do not need to be captured in the eCRFs.

7.2.9 Day 4 to 14: Postsurgical Safety Follow-up

Vital sign assessment, physical examination, review of medications, and AE monitoring will be performed. The post surgical treatment plan and TNM staging will be collected for all subjects. Clinical group will be collected for subjects with rhabdomyosarcoma.

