	institutional imaging protocol time of injection when po STATIC planar imaging sho minutes post injection. At least 15 minutes and r Lymphoseek injection, subjection	s. Imaging should begin at the erforming dynamic imaging. ould begin approximately 15 no more than 8 hours after ects will undergo surgery to	
	remove the primary tumor a during the lymphatic mappin with institutional practice, Lyn in the operating room immedi The injection of Lymphazur deemed appropriate by the su the standard of care at the samples will be collected for s surgery.	and all lymph nodes detected ag procedure. If in agreement mphazurin will be administered ately before or during surgery. in will only be performed as argeon and in accordance with clinical site. Blood and urine safety laboratory analyses post-	
	Safety follow-up (Day 4 to physical examination, and re performed between 4 to 14 da Postsurgical treatment plan; t (TNM) staging; and clinical gr	• 14): Vital sign assessment, eview of medications will be ys after Lymphoseek injection. tumor, lymph node, metastasis roup will be collected.	
	Adverse events (AE) will be r with the Baseline visit.	nonitored at each visit, starting	
Planned trial dates	Start of study August 2015	End of Study June 2021	
Planned number of trial centers / countries	Up to 10 sites in the United St	ates	
Number of subjects	For the primary analysis of safety, at least 27 subjects administered Lymphoseek will be evaluated:		
	• At least 6 subjects with me	elanoma	
	• At least 6 subjects with rha	abdomyosarcoma	
	Enrollment will be open to up other tumor types in which biopsy (SLNB) are appropriate	to 15 additional subjects with ILM and sentinel lymph node e.	
	At least 20 of the recruited sub	pjects will be ≤ 16 years of age.	
Safety endpoints Primary	Incidence of AEs		
Secondary	Changes over time in vitals signs, laboratory tests, and ECGs		
Diagnostic endpoints	 Proportion of subjects lymph nodes (i.e., localization) 	with Lymphoseek-identified tion)	

	• Number of Lymphoseek-identified lymph nodes per subject (i.e., degree of localization)
	• Proportion of subjects who underwent preoperative SPECT lymphoscintigraphy
	• Comparison of the number of lymph nodes detected with Lymphoseek intraoperatively to the number of nodes detected with preoperative SPECT

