	• Comparison of centralized, blinded pathologic assessment to local pathologic assessment of the excised lymph node(s) to confirm the presence/absence of tumor metastases on a per-subject and per-node basis
	• False negative rates and sensitivity for each detection method in subjects undergoing lymphadenectomy
	• Upstaging
	• Change in nodal staging before and after surgery based upon Lymphoseek-identified nodes (and Lymphazurin, if applicable)
	• Number of changes in treatment plan and relation to lymph nodes identified by Lymphoseek
	Additionally for those subjects receiving both Lymphoseek and Lymphazurin:
	• Proportion of subjects with Lymphazurin-identified lymph nodes (i.e., localization)
	• Number of Lymphazurin-identified lymph nodes per subject (i.e., degree of localization)
	• Proportion of lymph nodes (and subjects) identified intraoperatively by Lymphazurin that are also identified intraoperatively by Lymphoseek (i.e., nodal and per-subject concordance)
	• Proportion of lymph nodes identified intraoperatively by Lymphoseek that are also identified intraoperatively by Lymphazurin control (i.e., nodal and per-subject reverse concordance)
	• Difference between nodal and reverse nodal concordance
Plan for statistical analysis	Analysis populations:
	• Safety: all enrolled subjects with administration of Lymphoseek
	• Intent-to-treat (ITT): all enrolled subjects with administration of Lymphoseek (with or without

Lymphazurin) and complete intraoperative lymphatic mapping
• Blue intent-to-treat (BITT): all ITT subjects with administration of Lymphazurin prior to ILM
• Per protocol (PP): all ITT subjects without major protocol violations
All safety analyses will be conducted on the safety population. The analysis of the diagnostic endpoints will be conducted on ITT, BITT, and PP populations, as applicable.
AEs will be summarized using system organ class and preferred term by tumor type and overall for all subjects in the safety population. AEs will also be summarized by severity, relationship to investigational product, and relationship to study procedure. All AEs will be listed.
Summary statistics (mean, median, sample size, standard deviation, minimum, and maximum) will be computed on the raw and change from baseline values for each vital sign parameter, quantitative laboratory parameter, and ECG parameter by time point, for each tumor type and overall.

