The localization rate, degree of localization, difference in preoperative SPECT versus intraoperative localization, agreement proportions of central pathology assessment to local pathology assessment, false negative rates, sensitivity rates, and upstaging, along with 95% confidence intervals, will be computed for each tracer (as applicable) for each tumor type and overall.
The proportion of ITT subjects with preoperative SPECT performed, those who had a hot spot on scan, and the time from Lymphoseek injection to hot spot localization, will be summarized by tumor type and overall.
Changes in nodal staging will be assessed via shift tables.
Changes in treatment plan and relation to lymph nodes will be listed.
Concordance endpoint analysis: For the BITT population, the number and proportion of concordant lymph nodes (Lymphoseek to Lymphazurin) will be computed, and a statistical test to determine if the concordance rate is greater than 0.9 will be conducted. In order for the test of the nodal concordance endpoint to successfully reject the null hypothesis that the concordance rate is ≤ 0.9 , the lower boundary of the one-sided 95% exact binomial confidence

interval must exceed 0.9 in the BITT population. In-house and/or literature data indicating that nodes may be considered as an independent sample will supplement the analysis.
If the test of the concordance endpoint is met (i.e., the null hypothesis is rejected), then a test for superiority of concordance relative to the secondary diagnostic endpoint of reverse concordance will be conducted using McNemar's test. If the one-sided p-value of the test is <0.05, then the concordance rate of Lymphoseek to Lymphazurin will be shown to be significantly greater than the reverse concordance rate of Lymphazurin to Lymphoseek.
The per-subject concordance and per-subject reverse concordance will also be computed along with 95% confidence intervals using the BITT population.
No formal interim analyses will be conducted during this study.
Data listings and tables will be created on an interim basis for review by a Data and Safety Monitoring Committee (DSMC), which is further described in Section 9.11.

TABLE OF CONTENTS

SY	NOPS	IS		2
LIS	ST OF	IN-TE2	XT TABLES	13
LIS	ST OF	APPEN	NDICES	13
LIS	ST OF	ABBR	EVIATIONS AND DEFINITIONS OF TERMS	14
TR	IAL A	DMIN	ISTRATIVE STRUCTURE	16
LA	BORA	ATORII	ES AND OTHER INSTITUTIONS FOR TRIAL CONDUCT	16
1	INT	RODU	CTION	17
	1.1	Back	ground	17

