2.2 Secondary Objectives

- To assess the excised lymph node(s) to confirm: the presence/absence of tumor metastases; agent localization per tumor type; degree of localization (nodes per subject both intraoperatively and with preoperative SPECT.
- To determine the concordance of in vivo localization rates of Lymphoseek and Lymphazurin, a vital blue dye (VBD), in tissue excised and histologically confirmed as lymph nodes from those subjects receiving two mapping agents.
- To record the change of subject stage based on histopathology and make a descriptive assessment on change in treatment plan.

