9.6 Diagnostic Variables

9.6.1 Primary Diagnostic Variables

The primary diagnostic variables for this study are:

- Subject localization rate (defined as the proportion of subjects with Lymphoseekidentified lymph nodes)
- Number of lymph nodes identified intraoperatively by Lymphoseek per subject
- Proportion of subjects who underwent preoperative SPECT or SPECT/CT
- Proportion of subjects with a lymph nodes identified preoperatively using SPECT or SPECT/CT
- Number of lymph nodes identified preoperatively using SPECT or SPECT/CT
- Agreement of the number of nodes identified by preoperative SPECT or SPECT/CT to intraoperative localization
- Subject and nodal agreement of central pathology assessment with local pathology assessment of the excised lymph node(s) to confirm the presence/absence of tumor metastases
- Nodal false negative rate for Lymphoseek-identified nodes (using blinded central pathology assessment and local pathology assessment)
- Nodal sensitivity for Lymphoseek-identified nodes (using blinded central pathology assessment and local pathology assessment)
- Upstaging (defined as the proportion of patients with pathology-positive lymph nodes who had at least one pathology-positive lymph node that was identified by Lymphoseek and had no other pathology-positive lymph nodes [i.e., identified by any other method])
- Change in subject nodal staging before and after surgery based upon Lymphoseekidentified nodes
- Changes in treatment plan and relation to lymph nodes identified by Lymphoseek

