The nodal sensitivity will be computed for Lymphoseek as the number of pathology-positive lymph nodes identified intraoperatively by the tracer divided by the total number of pathology-positive lymph nodes. A 95% confidence interval will also be computed. Sensitivities also will be calculated separately for the blinded central pathology assessment and the local pathology assessment.

The number and proportion of subjects upstaged by Lymphoseek will be computed along with a 95% confidence interval, where upstaging by an individual tracer is defined as a subject who had at least one pathology-positive node identified by one tracer and no pathology-positive nodes identified by the other tracer.

The change in subject nodal staging will be assessed via shift tables. A shift table for Lymphoseek will be produced to show the number of subjects with each combination of presurgery and post-surgery nodal staging. Each subject's post-surgery staging will be based on the pathology results of those nodes identified by Lymphoseek. For the purposes of this analysis, a subject may have two different post-surgery nodal staging results, one based on Lymphoseek-identified nodes and the other based on Lymphazurin-identified nodes (see Section 9.9.6).

Changes in treatment plan and relation to lymph nodes identified by Lymphoseek will be listed.

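### Change in treatment plan is an endpoint, but the plan is scheduled for recording only after surgery, so there is no prospective pre-surgery plan to compare it with

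*Combined protocol and SAP*

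**What the plan says.** Change in treatment plan runs through the protocol from objective to analysis. A secondary objective in Section 2.2 is to "make a descriptive assessment on change in treatment plan". The synopsis lists as a diagnostic endpoint: "Number of changes in treatment plan and relation to lymph nodes identified by Lymphoseek". Section 9.6.1 places "Changes in treatment plan and relation to lymph nodes identified by Lymphoseek" among the primary diagnostic variables. The planned analysis is a listing. Section 9.9.5 states: "Changes in treatment plan and relation to lymph nodes identified by Lymphoseek will be listed", and the synopsis analysis plan agrees: "Changes in treatment plan and relation to lymph nodes will be listed".

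The plan itself is scheduled once. The synopsis methodology puts "Postsurgical treatment plan" under the safety follow-up. Section 7.2.9, which describes the Day 4 to 14 visit, says: "The post surgical treatment plan and TNM staging will be collected for all subjects". In Appendix 1 the Treatment Plan row carries one mark, in the follow-up column.

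Staging is handled differently. Section 7.2.1 collects TNM at screening. Section 8.1.3 requires TNM and clinical stage before surgery, then an update with the pathological stage afterwards. Appendix 1 marks staging at screening and at follow-up, and Section 9.9.5 says: "The change in subject nodal staging will be assessed via shift tables".

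**The concern.** A change is a difference between two states, and the schedule records one. A site that followed the visible protocol exactly would reach the end-of-study visit with a post-surgical plan and no prospectively recorded plan to set against it. The visible text does not define a change. It also does not say who decides that one occurred, or how it is tied to a node found by Lymphoseek.

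The missing comparator is the one that matters for this endpoint. Every eligible subject is clinically node negative at screening (Section 4.1.1), and Section 1.1 gives the guiding of later treatment as one benefit of sentinel node biopsy. The informative comparison is therefore with the treatment intended before node results. If the baseline is settled only at follow-up, it is settled after surgery, at the visit that also collects updated TNM. At stake is whether the count and listing can be interpreted as planned.

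**Working it through.** The plan gives no figure to reproduce, so the check traces every mention of the treatment plan through the objectives, endpoints, visit descriptions, Appendix 1 and analysis, with staging alongside.

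| Item | Before surgery | After surgery | Planned analysis |
|---|---|---|---|
| Cancer staging | 1 (Sections 7.2.1 and 8.1.3; Appendix 1, screening) | 1 (Sections 7.2.9 and 8.1.3; Appendix 1, follow-up) | Shift table |
| Treatment plan | 0 | 1 (synopsis; Section 7.2.9; Appendix 1, follow-up) | Listing (count in the synopsis) |

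1. *Screening.* The synopsis and Section 7.2.1 list eligibility, history, staging, performance status, vital signs, ECG, examination, laboratory tests and medications. No intended treatment is listed.
2. *Before enrollment and before injection.* Section 7.2.2 asks about changes in medical history and medications. Section 7.2.4 covers vital signs and syringe assay.
3. *Rest of Day 1.* Sections 7.2.6 and 7.2.7 cover vital signs, ECG, imaging, mapping and surgery.
4. *Nearest substitutes.* Inclusion criterion 2 requires that resection or biopsy is planned and mapping is appropriate; it does not record what treatment is intended afterwards. Clinical stage is a stage, and no visible section maps stage to plan across melanoma, rhabdomyosarcoma and the other tumors.
5. *Deferrals.* The visible deferrals to the SAP concern additional safety analyses (Section 9.9.4) and independence of nodes (Section 9.9.6). The SAP could define a change, but it could not supply a baseline that was not collected.
6. *Node side of the comparison.* Method of identification is recorded for each node and every removed node goes to pathology (Section 8.4.2). A central result is reported per node (Section 8.5.3). The inputs missing are the pre-surgery plan and the reason for a change.

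Pairs available: Sections 8.1.1 and 9.7 expect at least 25 of about 27 subjects to complete follow-up. At exactly 25, staging pairs number up to 25 × 1 = 25, and prospective plan pairs number 25 × 0 = 0. The ITT set may be smaller, because Section 9.9.1 requires eligibility and complete mapping. This restates the schedule; it does not estimate how many plans change.

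**The case against.** The commitment is modest. The objective asks for a descriptive assessment and the analysis is a listing, with no interval, test or decision rule, whereas neighbouring endpoints carry 95% confidence intervals. Section 3.1 says the follow-up visit is there to assess disease management. An investigator's judgement at that visit, read beside a documented shift in nodal stage, could support a narrative listing. The eCRF is described in a separate document (Section 10.1.1) and may ask directly whether the plan changed. All of this stands, and it limits the weight of the point. It does not supply a pre-surgery plan, and a question answered at follow-up is a judgement made after surgery.

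A reader might infer that reported changes would rest on memory. The documents do not show that. Section 10.1 requires protocol data to be in source documents, and a plan written in the chart before surgery would be contemporaneous evidence even if abstracted later. Whether such notes exist is not stated.

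A reader might also size the problem from the cited node-positivity rates. On 27 subjects, 6/28 gives 5.8 node-positive subjects and 25.6% gives 6.9, so one wrong call looks like 17% or 14% of them. This is not supported. It is one divided by an assumed number of node-positive subjects, whereas the endpoint is plan changes, and no visible figure says how often a positive node changes a plan. No rate is given for the other tumors. Section 1.1 also cites 81 of 592 in rhabdomyosarcoma, which gives 27 × 81/592 = 3.7 subjects and 1/3.7 = 27%, so the result depends on the rate chosen.

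**Conclusion.** The point holds as a gap between a stated endpoint and the scheduled data: 0 plan records before surgery and 1 after, while staging in the same objective has 1 and 1. It is more than a missing detail, because full compliance with the visible schedule still yields no prospective comparator.

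The reach is narrow. It touches one descriptive count and listing. Because Section 9.6.1 uses the word primary for its diagnostic variables, a reader might infer that the main result is at risk. It is not: the primary objective and endpoint are safety, and neither these nor the concordance test uses the treatment plan.

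The conclusion assumes that no document outside the visible protocol requires a plan to be recorded before surgery. Confidence is high on the reading of the schedule. How accurate a plan reconstructed at follow-up would be, and how many plans would change, cannot be judged from the documents. The gap merits correction because the remedy is small.

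**What to change.** For subjects still to be enrolled:

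- Add a Treatment Plan entry before Lymphoseek injection, in Section 7.2.1 or 7.2.4, with a matching mark in Appendix 1. Record the post-surgical treatment intended on the pre-surgery clinical stage.
- Define a change as a Day 4 to 14 plan that differs from that entry.
- Record the reason: pathology of a Lymphoseek-identified node, other surgical finding, or other. Rhabdomyosarcoma clinical group depends on completeness of resection as well as nodes (Section 8.1.3, Table 5), so a plan could differ for reasons unrelated to nodes. The listing should show node-driven changes separately from those due to margins or other causes.

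For subjects already treated, abstract any plan documented before surgery and flag it as retrospective. They would still have no prospective baseline.

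The cost is a formal amendment under Section 3.3, two eCRF fields (pre-surgery plan and reason for change) and source abstraction at up to 10 sites; the number already treated is not stated. No visit or procedure is added. This is a recording requirement only and implies nothing about which treatment should be chosen.
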